5.2.2. Secondary outcomes

Serious adverse events, access-related complications and vascular access thrombosis:

The number of access-related complications and access-related thromboses for each patient-year of haemodialysis treatment will be analysed using a general linear mixed effect model with Poisson distribution and identity link, and with time as off-set variable. The outcome will be expressed as a ratio (exponential of β_1) of events (number of interventions) per 1 unit increase of exposure time between both groups. A random intercept for each individual participant will be estimated to account for dependence of observations. Expected counts will be plotted against observed counts to check whether the distribution of counts follow a Poisson distribution. Furthermore, the Pearson dispersion statistic will be assessed to check whether there is equidispersion of the variance compared to the mean. In case of overdispersion of the data, a quasi-Poisson model or negative binomial model will be performed. Sensitivity analyses will be done for the primary outcome with major interventions having twice the weight of minor interventions, and with exclusion of patients with access-related interventions with technical failure (residual stenosis $>30\%$) and clinical failure (flow volume $<500\text{mL/min}$ in the first week after intervention and/or failure to restore vascular access function and clinical signs of flow dysfunction).

5.3. Missing data

Primary outcome data are not expected to be missing, as interventions on vascular access will be reported in the patients' medical files. We expect no loss to follow-up in the study participants since they are observed three times per week in the dialysis unit. Patient-reported outcomes will be

analysed using generalized estimating equations that allow for missing data. Other missing data will be handled by using 5 imputation cycles with regression methods. Outliers will not be removed from the analysis unless the data can clearly be shown to be erroneous.

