2.3. Sample size

Sample sizes were estimated for the number of interventions required for each patient-year of dialysis treatment (i.e. the primary outcome), which will be analysed using a general linear model with Poisson distribution and time as off-set variable. In the FLOW project, we aim to detect a difference in the intervention rate of 0.25 per year between study groups in a superiority analysis. This difference is associated with an economically relevant effect of saving approximately 1 million euros per year at a 75% de-implementation rate. The minimal clinically relevant difference in the intervention rate remains to be defined for this core outcome measure, but will likely be greater than 0.25 per year. In the Netherlands, the access-related intervention rate in hemodialysis patients with arteriovenous fistulas and grafts was 1.56 and 3.30 per year, respectively, in a retrospective observation cohort study in 10 dialysis units. As the distribution between fistulas and grafts is approximately 8:1, these figures amount to an average of 1.77 interventions per patient-year in the Netherlands. Since the study includes young hemodialysis patients waiting for kidney transplantation and old hemodialysis patients with limited life expectancy, 20% of participants are expected to leave the study per year before completing the follow-up period. A total follow-up time of 828 patient-years (414 patient-years in each treatment arm) achieves 80% power to detect a 0.25 decrease in the number of interventions per patient-year between the study groups using a two-sided, large-samples z-test of the Poisson event-rate difference at a significance level of 0.05. With a standard follow-up of 2 years and a drop-out rate of 20% per year, this would require a sample size of 518 patients. Implementing a variable follow-up time of a minimum of 2 years and a maximum of 3 years is expected to result in 162 additional patient-years. This corresponds to 101 patients with 2-years of follow-up and a drop-out rate of 20% per year, and therefore leads to a new sample size estimation of 417 patients. An interim analysis for safety requires a sample size of 144 patients (72 in each treatment arm) contributing 1 year of follow-up with an expected event rate of 0.5 events per patient-year to show non-inferiority with regards to access-related serious adverse events at a margin of 0.5 events per patient-year with a power of 90%.

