2.4. Framework

Superiority framework. The intervention group will be compared to the control group. Analyses will be stratified for treatment center and for vascular access type (graft vs fistula). Every effort is made to establish eligibility of participants prior to randomization; no withdrawals due to ineligibility are allowed and the analyses include all participants enrolled. The primary analysis will be on the intention to treat population (i.e. no participants are withdrawn from analysis for lack of adherence to treatment allocation); exploratory on-treatment analyses will be performed. A comparison of included and excluded patients is done to provide insight into the external validity of the clinical trial. Every effort is made to avoid missing data, including assistance from dialysis nurses in obtaining patient-reported outcome measures during dialysis sessions. Primary outcome data are not expected to be missing, as interventions on vascular access will be reported in the patients' medical files. We expect no loss to follow-up in the study participants since they are observed three times per week in the dialysis unit. Patient-reported outcomes will be analysed using generalized estimating equations that allow for missing data. Other missing data will be handled by using 5 imputation cycles with regression methods. Outliers will not be removed from the analysis unless the data can clearly be shown to be erroneous.

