Stratification for study site and vascular access type (fistula / graft).

Subgroup analysis: vascular access type (fistula / graft).

Sensitivity analysis:

- Exclusion of patients with interventions with technical failure (see Table 7A)
- Exclusion of patients with interventions with clinical failure (see Table 7A)

Table 4B: Access-related adverse events

	Monitoring (... patient-years)	Surveillance (...patient-years)	Event rate ratio (95% CI)	P
Access-related adverse events	N	N	... (....)	...
Pain requiring medication (days)	N	N	... (....)	...
Infection requiring antibiotics (days)	N	N	... (....)	...
Bleeding requiring blood transfusion	N	N	... (....)	...
Central venous catheter thrombolysis	N	N	... (....)	...

Statistical analysis (intention to treat population): general linear mixed effect model with Poisson distribution and identity link, and with time as off-set variable (see Table 3A for details).

Table 4C: Hospital admittance

	Monitoring (...patient-years)	Surveillance (...patient-years)	Event rate ratio (95% CI)	P
Hospital admittance (days)	N	N	... (...-...)	...
Related to vascular access	N	N	... (...-...)	...
Unrelated to vascular access	N	N	... (...-...)	...

Statistical analysis (intention to treat population): general linear mixed effect model with Poisson distribution and identity link, and with time as off-set variable (see Table 3A for details).

Table 4D: Line listing of serious adverse events

Table 4E: Line listing of protocol deviations

Table 5A: SF-VAQ scores at baseline

	All patients (N=...)	Monitoring (N=...)	Surveillance (N=...)	P
Total score
Physical domain
Pain
Bleeding
Swelling
Bruising
Social functioning domain
Daily activities
Appearance
Sleep
Bathing and showering
Dialysis complications domain
Problem on dialysis
Access care
Hospitalization
Worry about access longevity

Groups are based on initial randomization

Include only questionnaires with complete data. Questions are Likert scores from 1 to 7. Domain scores are the sum of the 4 questions. The total score is the sum of the 3 domains.

Statistical analysis: Students t-test.

Table 5B: SF-VAQ scores according to the number of interventions during follow-up

	No interventions during follow-up (N=...)	1 intervention during follow-up (N=...)	>1 intervention during follow-up (N=...)	P
Total score
Physical domain
Pain
Bleeding
Swelling
Bruising
Social functioning domain
Daily activities
Appearance
Sleep
Bathing and showering
Dialysis complications domain

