Problem on dialysis
Access care
Hospitalization
Worry about access longevity

Include only questionnaires with complete data. Questions are Likert scores from 1 to 7. Domain scores are the sum of the 4 questions. The total score is the sum of the 3 domains.

Sensitivity analysis: exclude patients with interventions on the current vascular access before enrollment

Statistical analysis: mixed linear model

Table 5C: Change in SF-VAQ scores with access-related interventions

	Before intervention (>30 days)	Around intervention (30 days before – 90 days after)	P	Clinically relevant change
Total score	Mean (SD)	Mean (SD)	...	%
Physical domain	Mean (SD)	Mean (SD)	...	%
Pain	Mean (SD)	Mean (SD)	...	
Bleeding	Mean (SD)	Mean (SD)	...	
Swelling	Mean (SD)	Mean (SD)	...	
Bruising	Mean (SD)	Mean (SD)	...	
Social functioning domain	Mean (SD)	Mean (SD)	...	%
Daily activities	Mean (SD)	Mean (SD)	...	
Appearance	Mean (SD)	Mean (SD)	...	
Sleep	Mean (SD)	Mean (SD)	...	
Bathing and showering	Mean (SD)	Mean (SD)	...	
Dialysis complications domain	Mean (SD)	Mean (SD)	...	%
Problem on dialysis	Mean (SD)	Mean (SD)	...	
Access care	Mean (SD)	Mean (SD)	...	
Hospitalization	Mean (SD)	Mean (SD)	...	
Worry about access longevity	Mean (SD)	Mean (SD)	...	

Compare SF-VAQ scores before (latest but >30 days before) and around (closest to the intervention but <30 days before and <90 days after) the access-related intervention. Calculate the proportion of patients with a clinically relevant change in SF-VAQ scores.

The clinically relevant change in SF-VAQ scores is defined as 0.5 times the standard deviation of the difference in SF-VAQ scores between two adjacent measurements in patients without vascular access-related interventions or vascular access-related (serious) adverse events.

Statistical analysis: paired Student t-test

Table 5D: Change in SF-VAQ scores with thrombosis

	Before thrombosis (>30 days)	After thrombosis (<90 days)	P	Clinically relevant change
Total score	Mean (SD)	Mean (SD)	...	%
Physical domain	Mean (SD)	Mean (SD)	...	%
Pain	Mean (SD)	Mean (SD)	...	
Bleeding	Mean (SD)	Mean (SD)	...	
Swelling	Mean (SD)	Mean (SD)	...	
Bruising	Mean (SD)	Mean (SD)	...	
Social functioning domain	Mean (SD)	Mean (SD)	...	%
Daily activities	Mean (SD)	Mean (SD)	...	
Appearance	Mean (SD)	Mean (SD)	...	
Sleep	Mean (SD)	Mean (SD)	...	
Bathing and showering	Mean (SD)	Mean (SD)	...	
Dialysis complications domain	Mean (SD)	Mean (SD)	...	%
Problem on dialysis	Mean (SD)	Mean (SD)	...	

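### GEE as specified does not by itself deal with SF-VAQ and EQ-5D-5L questionnaires whose absence depends on earlier scores

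*SAP*

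**What the plan says.** SAP section 2.4 states: "Patient-reported outcomes will be analysed using generalized estimating equations that allow for missing data". Section 5.3 repeats that these outcomes will be "analysed using generalized estimating equations that allow for missing data" and continues: "Other missing data will be handled by using 5 imputation cycles with regression methods". The word 'other' leaves SF-VAQ and EQ-5D-5L outside the imputation. Neither section gives a working correlation, weights, a covariate set or an assumption about why questionnaires are missing. Section 5.4 refers sensitivity analyses back to section 5.2, which has none for patient-reported outcomes or for missing data. No table shell in section 6 shows the GEE comparison of arms over time.

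Section 2.7 schedules the questionnaires at baseline and quarterly to month 24. Section 2.3 says that "20% of participants are expected to leave the study per year before completing the follow-up period" and explains this by the inclusion of "young hemodialysis patients waiting for kidney transplantation and old hemodialysis patients with limited life expectancy". Section 5.3 also says: "We expect no loss to follow-up in the study participants since they are observed three times per week in the dialysis unit". Under sections 2.1 and 4.4.2, patients are censored at transplantation, a change to peritoneal dialysis or the end of hemodialysis, and data are used only up to withdrawal.

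**The concern.** The SAP treats GEE as if the method itself took care of missing data. It does so only in a limited sense. GEE can be fitted when patients contribute different numbers of visits, but its estimating equations use the observed scores as they stand. If a patient's chance of returning the next form depends on the score on the last one, the observed scores no longer represent the group, and unweighted GEE is not in general consistent.

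That dependence is plausible here. A patient who feels unwell, or is dissatisfied with the access, may be less willing to fill out another form. The reason given for expecting no loss, three dialysis sessions a week, is persuasive for interventions recorded in medical files. It is less so for a voluntary questionnaire, because a patient can be present and still decline. At stake is the comparison of access satisfaction and health-related quality of life between the arms. These are secondary outcomes; the primary outcome is not affected.

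**Working it through.** **Step 1. The plan's own attrition figure (section 2.3).** With 20% leaving per year, the plan counts 2 × 0.8 = 1.6 patient-years per patient.
- 828 / 1.6 = 517.5, rounded up to 518.
- 162 / 1.6 = 101.25, or 101.
- 518 − 101 = 417.

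All three figures reproduce.

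**Step 2. What this implies at month 24.**
- Compounded: 1 − 0.8² = 0.36 have left.
- Linear: 2 × 0.20 = 0.40 have left.

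So 60% to 64% are still in the trial, before any skipped forms. The SAP does not divide the leavers into deaths, planned censoring and other withdrawals, and it gives no rate of skipped questionnaires. The amount of truly missing data therefore cannot be computed.

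**Step 3. Illustrative simulation.** From the SAP: 9 visits and a dropout of 1 − 0.8^(1/4) = 5.4% per quarter. Assumed:
- 300,000 patients in two fixed arms, true arm difference 0.30 at month 24;
- random intercept SD 0.7, random slope SD 0.08 per visit, residual SD 0.5;
- log-odds of dropout rising by 0.5 or 1.0 per unit fall in the previous score;
- exchangeable correlation set at 0.6;
- the weighted analysis given the true dropout probabilities, and the likelihood model the true covariance.

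The score SD is √(0.7² + 0.5²) = 0.86 at baseline and √(0.49 + 0.08² × 64 + 0.25) = 1.07 at month 24, so one unit is close to one SD. Dropout by month 24 was about 35% to 38% per arm.

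| Dropout depends on previous score | Log-odds | GEE, independence | GEE, exchangeable | Weighted GEE | Likelihood model |
|---|---|---|---|---|---|
| No (completely at random) | 0 | 0.303 | 0.300 | 0.303 | 0.299 |
| Both arms | 0.5 | 0.290 | 0.299 | 0.299 | 0.301 |
| Both arms | 1.0 | 0.272 | 0.294 | 0.301 | 0.302 |
| One arm only | 0.5 | 0.163 | 0.278 | 0.313 | 0.311 |
| One arm only | 1.0 | 0.034 | 0.243 | 0.306 | 0.305 |

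Errors against 0.30:
- Same mechanism in both arms: 0.010 to 0.028 with independence, 0.001 to 0.006 with exchangeable.
- One arm only: 0.137 to 0.266 with independence, 0.022 to 0.057 with exchangeable.

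Each row is a single simulated data set. With about 96,000 patients per arm left at month 24, the standard error is roughly 1.07 × √(2/96,000) = 0.005, so departures of about 0.01 in the last two columns are not evidence of bias.

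**Step 4. A second simulation.** This had no true effect, score-dependent dropout in one arm only, and about half the patients observed at month 24, which is heavier loss than step 2 implies. At log-odds 0.5 and 1.0 the false difference was:
- independence: 0.149 and 0.288 SD;
- exchangeable: −0.041 and −0.048 SD, the opposite sign;
- mixed model with unstructured covariance: −0.006 and −0.002 SD.

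Both simulations keep patients in one arm throughout. They show how the error arises, but they do not predict its size in this trial.

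**The case against.** The other side has several good points.

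**The SAP does not say that the GEE is unweighted.** This is true: it is inferred from silence. What can be supported is that the stated method, taken as written, lacks what it would need. Requiring data missing completely at random is also slightly too strict, because GEE remains valid if missingness depends only on modelled covariates. The SAP names none.

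**Large bias needs different mechanisms in the two arms.** This stands. Section 2.1 describes the trial as double-blind, and nothing in the SAP suggests that skipping depends on scores in one arm only. With no true effect and the same mechanism in both arms, the false difference is zero by symmetry. Section 2.4 also plans help from dialysis nurses to avoid missing questionnaires.

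**Leaving the study is not the same as missing data.** This also stands. A reader might infer that 36% to 40% of the month-24 scores are missing. Much of the expected leaving is death or planned censoring. After death there is no score, and after transplantation satisfaction with a dialysis access is no longer the question. A mixed model that implicitly carries scores past these events is not plainly better than GEE.

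**The questionnaire tables do not strengthen the case.** A reader might take "Statistical analysis: mixed linear model" under Table 5B as a sign that the authors themselves prefer another method for the arm comparison. That table compares patients by number of interventions, not by arm. A reader might likewise infer from "Include only questionnaires with complete data" that many forms are lost to the between-arm analysis. The rule is attached to Tables 5A, 5B and 5E, none of which compares arms over time, and the SAP gives no rate of missing items from which to compute a loss.

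**Conclusion.** The point holds as a gap in specification with a real statistical consequence. The SAP relies on GEE alone for missing questionnaires, and as written that does not cover missingness that depends on earlier scores.

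The likely size is small: 0.27 to 0.30 against a true 0.30 when the mechanism is the same in both arms. If it differed by arm, the error would be about 0.02 to 0.06 with an exchangeable working correlation and could approach 0.3 SD with independence. The plan does not say which would be used.

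A reader might infer that dropout alone is likely to create a between-arm difference of 0.15 to 0.29 SD. The SAP does not support that. Those values need one-arm score-dependent dropout, an independence working correlation and only half the patients retained at month 24, against the 60% to 64% that section 2.3 implies. All sizes rest on assumed variances and dropout models.

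**What to change.** In sections 2.4 and 5.3:

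1. Separate questionnaires missing while the patient is alive and on hemodialysis in the trial from scores that do not exist or are out of scope after death, transplantation or another planned censoring event. Do not impute or extrapolate past those events.
2. For the first group, state a missing-at-random assumption and name one method that is valid under it: inverse-probability-weighted GEE, multiple imputation using earlier scores followed by GEE (extending the imputation already planned), or a likelihood-based mixed model. If GEE is kept, name the working correlation.
3. Code current allocation as time-varying. Table 2L refers to subsequent randomization, Figure 2E to patients shifting between groups, and section 5.2.1 to events in the same person under both arms. A model with a fixed arm-by-visit term would ignore this.
4. Add one sensitivity analysis under missing not at random.

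The cost is a few sentences of SAP text, slightly more analysis work, and reliance on a model for missingness or for the scores. Data collection does not change.

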5.4. Additional analyses

Sensitivity analysis have already been described in section 5.2

5.4.1. Interim analysis

Interim analysis has already been described in section 2.5 and uses the same statistical techniques as described in section 5.2.2.

5.5. Harms

Safety endpoints are vascular access related (serious) adverse events (including vascular access thrombosis and abandonment). Statistical analysis of these endpoints have been described in section 5.2.2.

5.6. Statistical software

Statistical analysis will be done with the latest available version of R.

Table 9A: Cannulation practice – comparison between study groups (p. 64)

Table 9B: Cannulation practice – predictors of cannulation problems (p. 65)

Table 1A: Baseline characteristics - demographics

	All patients (N=...)		Monitoring (N=...)		Surveillance (N=...)		P
Sex (male)	%	(N)	%	(N)	%	(N)	...
Age (years)	Mean \pm SD	(N)	Mean \pm SD	(N)	Mean \pm SD	(N)	...
Body mass index (kg/m ²)	Mean \pm SD	(N)	Mean \pm SD	(N)	Mean \pm SD	(N)	...
Race		(N)		(N)		(N)	...
White	%	(N)	%	(N)	%	(N)	
Black	%	(N)	%	(N)	%	(N)	
Asian	%	(N)	%	(N)	%	(N)	
Other	%	(N)	%	(N)	%	(N)	
Cause of end-stage renal disease		(N)		(N)		(N)	...
Diabetes	%	(N)	%	(N)	%	(N)	
Vascular/hypertension	%	(N)	%	(N)	%	(N)	
Glomerulonephritis	%	(N)	%	(N)	%	(N)	
Polycystic kidney disease	%	(N)	%	(N)	%	(N)	
Interstitial nephritis	%	(N)	%	(N)	%	(N)	
Congenital/hereditary	%	(N)	%	(N)	%	(N)	
Systemic disease	%	(N)	%	(N)	%	(N)	
Other	%	(N)	%	(N)	%	(N)	
Unknown	%	(N)	%	(N)	%	(N)	
Smoking history		(N)		(N)		(N)	...
Current	%	(N)	%	(N)	%	(N)	
Stopped	%	(N)	%	(N)	%	(N)	
Never	%	(N)	%	(N)	%	(N)	
Use of antithrombotics		(N)		(N)		(N)	...
No	%	(N)	%	(N)	%	(N)	
Antiplatelet therapy	%	(N)	%	(N)	%	(N)	
Anticoagulant therapy	%	(N)	%	(N)	%	(N)	
Fish oil supplements	%	(N)	%	(N)	%	(N)	...
Serum albumin (g/L)	Mean \pm SD	(N)	Mean \pm SD	(N)	Mean \pm SD	(N)	...
Mobility		(N)		(N)		(N)	...
Independent (with cane or walker if needed)	%	(N)	%	(N)	%	(N)	
With help of other person	%	(N)	%	(N)	%	(N)	
Wheelchair	%	(N)	%	(N)	%	(N)	

Groups are based on initial randomization

Statistical analysis: Chi squared tests for categorical variables and Student t-test for continuous variables

Table 1B: Baseline characteristics – comorbidities

	All patients (N=...)		Monitoring (N=...)		Surveillance (N=...)		P
Hypertension	%	(N)	%	(N)	%	(N)	...
Diabetes mellitus	%	(N)	%	(N)	%	(N)	...
Ischemic cardiac disease		(N)		(N)		(N)	...
No	%	(N)	%	(N)	%	(N)	
Yes, with myocardial infarction	%	(N)	%	(N)	%	(N)	
Yes, without myocardial infarction	%	(N)	%	(N)	%	(N)	
Heart failure		(N)		(N)		(N)	...
No	%	(N)	%	(N)		(N)	
NYHA 1	%	(N)	%	(N)	%	(N)	
NYHA 2	%	(N)	%	(N)	%	(N)	
NYHA 3	%	(N)	%	(N)	%	(N)	
NYHA 4	%	(N)	%	(N)	%	(N)	
Arrhythmia	%	(N)	%	(N)	%	(N)	...
Pacemaker	%	(N)	%	(N)	%	(N)	...
Cerebrovascular disease	%	(N)	%	(N)	%	(N)	...
Peripheral arterial disease		(N)		(N)		(N)	...
No	%	(N)	%	(N)	%	(N)	
Rutherford stage 1-3	%	(N)	%	(N)	%	(N)	
Rutherford stage 4-6	%	(N)	%	(N)	%	(N)	
Chronic pulmonary disease	%	(N)	%	(N)	%	(N)	...
Active malignancy		(N)		(N)		(N)	...
No	%	(N)	%	(N)	%	(N)	
Solid malignancy	%	(N)	%	(N)	%	(N)	
Hematologic malignancy	%	(N)	%	(N)	%	(N)	
Psychiatric disease	%	(N)	%	(N)	%	(N)	...

Groups are based on initial randomization

Statistical analysis: Chi squared tests for categorical variables

Table 1C: Baseline characteristics – dialysis history

	All patients (N=...)		Monitoring (N=...)		Surveillance (N=...)		P
Time on renal replacement therapy (months)	Median \pm IQR	(N)	Median \pm IQR	(N)	Median \pm IQR	(N)	...
Time on hemodialysis (months)	Median \pm IQR	(N)	Median \pm IQR	(N)	Median \pm IQR	(N)	...
Dialysis treatments per week	Mean \pm SD	(N)	Mean \pm SD	(N)	Mean \pm SD	(N)	...
Vascular access type		(N)		(N)		(N)	...
Arteriovenous fistula	%	(N)	%	(N)	%	(N)	...
Radiocephalic fistula	%	(N)	%	(N)	%	(N)	
Brachiocephalic fistula	%	(N)	%	(N)	%	(N)	
Brachiobasilic fistula	%	(N)	%	(N)	%	(N)	
Other fistula configuration	%	(N)	%	(N)	%	(N)	
Baseline diameter outflow vein (mm)	Median \pm IQR	(N)	Median \pm IQR	(N)	Median \pm IQR	(N)	...
Arteriovenous graft	%	(N)	%	(N)	%	(N)	...
Forearm loop graft	%	(N)	%	(N)	%	(N)	
Upper arm straight graft	%	(N)	%	(N)	%	(N)	
Upper arm loop graft	%	(N)	%	(N)	%	(N)	
Other graft configuration	%	(N)	%	(N)	%	(N)	
Age vascular access (months)	Median \pm IQR	(N)	Median \pm IQR	(N)	Median \pm IQR	(N)	...
Vascular access side (left)	%	(N)	%	(N)	%	(N)	...
Previous vascular access	%	(N)	%	(N)	%	(N)	...
Previous vascular access interventions	%	(N)	%	(N)	%	(N)	...
Baseline access flow (mL/min)	Median \pm IQR	(N)	Median \pm IQR	(N)	Median \pm IQR	(N)	...

Groups are based on initial randomization

Statistical analysis: Chi squared tests for categorical variables, Student t-test for continuous variables with normal distribution, and Mann-Whitney U-test for continuous variables deviating from normal distribution

Figure 1D: Access flow distribution in screened population

Exclude home hemodialysis patients and patients with central venous catheters

Table 1E: Comparison of enrolled patients with normal and high-flow vascular access

	Normal flow (<1500 mL/min) (N=...)		High flow (>1500 mL/min) (N=...)		P
Age (years)	Mean (SD)	N	Mean (SD)	N	...
Sex (male)	%	N	%	N	...
Hypertension	%	N	%	N	...
Diabetes mellitus	%	N	%	N	...
Ischemic cardiac disease		N		N	...
No	%	N	%	N	
Yes, with myocardial infarction	%	N	%	N	
Yes, without myocardial infarction	%	N	%	N	
Heart failure		N		N	...
No	%	N	%	N	
NYHA 1	%	N	%	N	
NYHA 2	%	N	%	N	
NYHA 3	%	N	%	N	
NYHA 4	%	N	%	N	
Cerebrovascular disease	%	N	%	N	...
Peripheral arterial disease		N		N	...
No	%	N	%	N	
Rutherford stage 1-3	%	N	%	N	
Rutherford stage 4-6	%	N	%	N	
Vascular access		N		N	...
Fistula	%	N	%	N	...
Radiocephalic	%	N	%	N	
Brachiocephalic	%	N	%	N	
Brachiobasilic	%	N	%	N	
Graft	%	N	%	N	

Table 2A: Trial screening and enrollment log

	Prevalent hemodialysis patients	
	N	%
Total		
Exclusion criteria		
Home hemodialysis		
Central venous catheter		
Informed consent not possible		
Planned kidney transplantation < 6 months		
Life expectancy < 6 months		
Transfer to another dialysis unit <6 months		
Enrolled in another vascular access trial		
Vascular access thrombosis in the past year		
Vascular access flow <500 mL/min		
Planned vascular access-related intervention		
Vascular access not functional ^a		
Multiple outflow veins in cannulation zone		
Total study candidates		
No informed consent		
Unwilling to participate in trials		
Feeling insecure with blind flow measurements		
Total participants		

Table 2B: Comparison of enrolled patients with unselected hemodialysis population - Baseline characteristics

	Unselected population (N=...)		Enrolled patients (N=...)		P
Sex (male)	%	N	%	N	...
Age (years)	Mean \pm SD	N	Mean \pm SD	N	...
Body mass index (kg/m ²)	Mean \pm SD	N	Mean \pm SD	N	...
Cause of end-stage renal disease		N		N	...
Diabetes	%	N	%	N	
Vascular/hypertension	%	N	%	N	
Glomerulonephritis	%	N	%	N	
Polycystic kidney disease	%	N	%	N	
Interstitial nephritis	%	N	%	N	
Congenital/hereditary	%	N	%	N	
Systemic disease	%	N	%	N	
Other	%	N	%	N	
Unknown	%	N	%	N	
Comorbidities					
Diabetes mellitus	%	N	%	N	...
Ischemic cardiac disease	%	N	%	N	...
Heart failure	%	N	%	N	...
Cerebrovascular disease	%	N	%	N	...
Peripheral arterial disease	%	N	%	N	...
Chronic pulmonary disease	%	N	%	N	...
Active malignancy	%	N	%	N	...
Psychiatric disease	%	N	%	N	...
Time on hemodialysis (months)	Median \pm IQR	N	Median \pm IQR	N	...
Vascular access type		N		N	...
Arteriovenous fistula	%	N	%	N	
Arteriovenous graft	%	N	%	N	

Patients with home hemodialysis and central venous catheters are excluded.

Statistical analysis: Chi squared tests for categorical variables, Student t-test for continuous variables with normal distribution, and Mann-Whitney U-test for continuous variables deviating from normal distribution

Table 2C: Comparison of enrolled patients with unselected hemodialysis population - Vascular-access related interventions and serious adverse events

	Unselected population (... patient-years)	Enrolled population (...patient-years)	Event rate ratio (95% CI)	P
Interventions for flow dysfunction	N	N	... (....)	...
Percutaneous interventions	N	N	... (....)	...
Balloon angioplasty without stent	N	N	... (....)	...
Balloon angioplasty with stent	N	N	... (....)	...
Percutaneous thrombectomy	N	N	... (....)	...
Surgical interventions	N	N	... (....)	...
Open thrombectomy	N	N	... (....)	...
Patch angioplasty	N	N	... (....)	...
Revision of anastomosis	N	N	... (....)	...
New arteriovenous fistula	N	N	... (....)	...
New arteriovenous graft	N	N	... (....)	...
Ligation of arteriovenous fistula	N	N	... (....)	...
Ligation of arteriovenous graft	N	N	... (....)	...
Central venous catheter interventions	N	N	... (....)	...
Catheter insertion	N	N	... (....)	...
Guidewire exchange	N	N	... (....)	...
Catheter removal	N	N	... (....)	...
Other vascular access interventions	N	N	... (....)	...
Repair (pseudo)aneurysm	N	N	... (....)	...
Ligation of accessory vein	N	N	... (....)	...
Embolisation of accessory vein	N	N	... (....)	...
Superficialisation	N	N	... (....)	...
Distal revision and interval ligation	N	N	... (....)	...
Proximalisation of arterial inflow	N	N	... (....)	...
Revision using distal inflow	N	N	... (....)	...
Banding	N	N	... (....)	...
Serious adverse events				
Thrombosis	N	N	... (....)	...
Access abandonment	N	N	... (....)	...

Statistical analysis: Poisson test with time as offset variable.

Figure 2D: Comparison of enrolled patients with unselected hemodialysis population - Survival

Kaplan-Meier survival curve of unselected hemodialysis population and enrolled patients

Statistical analysis: Log rank test

Figure 2E: Patient allocation to study groups

X-axis: time (1-1095 days)

Y-axis: patients (N=375)

The grid is filled with colors: red when allocated to the monitoring group, blue when allocated to the surveillance group, and grey after the end of the study (different shades of grey may be considered for different reasons to end study participation)

Patients will be ordered according the time of shifting between groups to facilitate interpretation (with patients who remained in the monitoring group the entire study duration at the top of the grid, and patients who remained in the surveillance group the entire study duration at the bottom of the grid)

Table 2F: Vascular access dysfunction detected by monitoring and surveillance - Available measurements

	Monitoring		Surveillance	
	N	Follow-up	N	Follow-up
Monitoring reports ^a person-years person-years
Flow measurements person-years person-years

Table 2G: Vascular access dysfunction detected by monitoring and surveillance - Monitoring reports

	Monitoring (... reports)	Surveillance (... reports)	P
Clinical indicators of flow dysfunction	%	%	...
Physical examination	%	%	...
Weak or discontinuous thrill	%	%	...
High pitched or discontinuous bruit	%	%	...
Hyperpulsatile vascular access	%	%	...
Weak vascular access	%	%	...
No thrill or bruit	%	%	...
Recurrent problems during dialysis	%	%	...
Inability to achieve target blood flow	%	%	...
New cannulation problems	%	%	...
Prolonged bleeding	%	%	...
Unexplained fall in dialysis efficiency	%	%	...
Other findings at inspection			
Aneurysm	%	%	...
Hand ischemia	%	%	...
Infection	%	%	...
Edema	%	%	...
Skin lesions	%	%	...
Hematoma	%	%	...

Statistical analysis: Chi squared tests.

Table 2H: Vascular access dysfunction detected by monitoring and surveillance - Surveillance flow measurements

	Monitoring (... measurements)	Surveillance (... measurements)	P
Access flow <500 mL/min ^b	%	%	...
With clinical indicators of flow dysfunction	%	%	...
Without clinical indicators of flow dysfunction	%	%	...
Access flow 500-1000 mL/min with >20% reduction from baseline ^c	%	%	...
With clinical indicators of flow dysfunction ^d	%	%	...
Without clinical indicators of flow dysfunction ^d	%	%	...

Data are presented as proportions. The sum of the proportions may not add up to 100% because patients may have more than one clinical indicator of flow dysfunction.

^a Monitoring reports were not transferred to the research database in two study sites (OLVG and MUMC+ from 11-2024 onwards) because of technical issues with the electronic patient files.

^b Access flow is considered <500 mL/min only when the initial low flow measurement was confirmed in a subsequent dialysis session.

^c Baseline is the first flow measurement after randomization.

[figure not shown]
^d Clinical indicators of flow dysfunction refer to the decision rules for interventions defined in the study protocol (used to send notifications to the study sites).

When counting flow measurements, only measurements for surveillance and confirmatory measurements after low flow are counted. Flow measurements to evaluate interventions or as random repeats are excluded from analysis.

[figure not shown]
Statistical analysis: Chi squared tests.

Flow chart 2I: Consequence of flow dysfunction detected by monitoring and surveillance

Monitoring reports

Surveillance flow measurements (only for patients allocated to the surveillance group)

Listing of reasons for:

- Flow dysfunction for reasons other than recorded in registration of flow dysfunction
- Decision by the study team not to act on low flow measurement (PROTOCOL VIOLATION)

Clinical indicators of flow dysfunction refer to the decision rules for interventions defined in the study protocol (used to send notifications to the study sites).

No significant findings on duplex ultrasounds is defined as the absence of hemodynamically significant stenosis AND no clinically significant stenosis as determined by multidisciplinary review.

Table 2J: Time between surveillance flow measurements

	Monitoring		Surveillance		P
Time between regular flow measurements	Median (IQR)	N	Median (IQR)	N	...
>6 weeks	%		%		...
Thrombosis during delay	-		%		
Time until confirmatory flow measurement for low flow	Median (IQR)	N	Median (IQR)	N	...
>1 week	%		%		...
Thrombosis during delay	-		%		

Statistical analysis: Mann-Whitney U-test comparing median time between monitoring and surveillance groups; Chi squared test for categorical variables.

Table 2K: Time between indication and intervention

	Monitoring (N=...)				Surveillance (N=...)				P
	Median (IQR)	N	>1 week	Thrombosis in waiting time	Median (IQR)	N	>1 week	Thrombosis in waiting time	
All cases			%	%			%	%	...
Indications									
Clinical indicators of flow dysfunction			%	%			%	%	...
Access flow <500 mL/min without clinical indicators of flow dysfunction	-	-	-	-			%	%	
Interventions									
Percutaneous interventions			%	%			%	%	...
Open surgical interventions			%	%			%	%	...

Interventions for thrombosis outside the waiting time for interventions for clinical indicators of flow dysfunction or access flow <500 mL/min (in the surveillance group) are excluded.

Statistical analysis: Mann-Whitney U-test comparing median time between monitoring and surveillance groups.

Table 2L: Time between intervention and subsequent randomization

	Monitoring		Surveillance		P
Time between intervention and assessment of clinical success	Median (IQR)	N	Median (IQR)	N	...
>4 weeks	%		%		...
Thrombosis during delay	%		%		...
Time between confirmation of clinical success and subsequent randomization ^a	Median (IQR)	N	Median (IQR)	N	...
>2 weeks	%		%		...
Thrombosis during delay	%		%		...

Interventions resulting in or from vascular access abandonment are excluded.

^a Only for interventions with clinical success.

Statistical analysis: Mann-Whitney U-test comparing median time between monitoring and surveillance groups; Chi squared test for categorical variables.

Table 2M: Duplex ultrasound for vascular access flow dysfunction - Available measurements

	Monitoring (... person-years)	Surveillance (... person-years)	Event rate ratio (95% CI)	P
Duplex ultrasound for clinical indicators of flow dysfunction ^a	N	N	... (...-...)	...
Duplex ultrasound for access flow <500 mL/min without clinical indicators of flow dysfunction ^a	N	N	... (...-...)	...
Duplex ultrasound not for flow dysfunction	N	N	... (...-...)	...

Statistical analysis: general linear mixed effect model with Poisson distribution and identity link, and with time as off-set variable (see Table 3A for details).

Table 2N: Findings of duplex ultrasound for flow dysfunction

	All patients (N=...)		Monitoring (N=...)		Surveillance (N=...)		P
Access flow (mL/min)	... + SD	N	... + SD	N	... + SD	N	...
Diameter outflow vein (mm) ^b	... + SD	N	... + SD	N	... + SD	N	...
Stenosis		N		N		N	...
None	%	N	%	N	%	N	
Single	%	N	%	N	%	N	
Multiple	%	N	%	N	%	N	
Stenosis characteristics ^c							
Location		N		N		N	...
Fistulas	%	N	%	N	%	N	...
Arterial inflow	%	N	%	N	%	N	
Juxta-anastomotic vein	%	N	%	N	%	N	
Outflow vein	%	N	%	N	%	N	
Graft	%	N	%	N	%	N	...
Arterial inflow	%	N	%	N	%	N	
Juxta-anastomotic arterial	%	N	%	N	%	N	
In graft	%	N	%	N	%	N	
Juxta-anastomotic venous	%	N	%	N	%	N	
Outflow vein	%	N	%	N	%	N	
Vessel diameter							
Stenosis (mm)	... + SD	N	... + SD	N	... + SD	N	...
Reference vessel (mm)	... + SD	N	... + SD	N	... + SD	N	...
Diameter reduction (%)	... + SD	N	... + SD	N	... + SD	N	...
Peak systolic velocity							
Stenosis (cm/s)	... + SD	N	... + SD	N	... + SD	N	...
Reference vessel (cm/s)	... + SD	N	... + SD	N	... + SD	N	...
PSV ratio	... + SD	N	... + SD	N	... + SD	N	...
Hemodynamic significance (yes)	%	N	%	N	%	N	...

^a Clinical indicators of flow dysfunction refer to the decision rules for interventions defined in the study protocol (and used to send notifications to the study sites).

^b Mean of diameter proximal / mid / distal outflow vein.

^c For multiple stenosis, the most severe stenosis (i.e. highest PSV-ratio) is chosen.

Statistical analysis: Chi squared tests for categorical variables and Student t-test for continuous variables

Table 2O: End of study

